3 OBJECTIVES AND ENDPOINTS

OBJECTIVES	ENDPOINTS	JUSTIFICATION FOR ENDPOINTS	PUTATIVE MECHANISMS OF ACTION
Primary			
The primary objective is to understand the outcome of using the at-home intracervical insemination Mosie kit, i.e. pregnancy rate after its use.	The primary endpoints is: Pregnancy Rate after up to 6 cycles. Another primary end point is to understand the rates of pregnancy in people who desire to get pregnant without intercourse (i.e. both single and those in LGBTQ relationships.	The ultimate objective of using the Mosie Kit is to end up pregnant. Thus pregnancy rate is a primary endpoint. Specifically, pregnancy rate in up to 6 (six) cycles will be examined as it is the typical standard timeframe for attempting to get pregnant using IVI or IUI before seeking an alternative method. People who have no known fertility issue who are trying to conceive without intercourse such as those who are in LGBTQ relationships or those who are not in any relationship at all will likely have higher pregnancy rates than those with known fertility issues of female origin. Women in LGBTQ relationships wishing to conceive might also have a higher pregnancy rate than those in heterosexual relationships where infertility might be caused by things like low sperm count, sperm motility issues or erectile dysfunction (ED).	The Mosie Kit is intended to be used to deposit semen at or near the cervix where the sperm will have an increased likelihood of entering the uterus and pairing up with the ovum resulting in a pregnancy. Pregnancy rates increase when sperm reaches the ovum and fertilizes it. In people with no known fertility issues, the Mosie kit deposits the semen where it is able to fertilize the ovum. People without infertility issues who want to get pregnant without sex by using the Mosie Baby are also more likely than people with known fertility issues to get pregnant.

Secondary			

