4 STUDY DESIGN

4.1 Overall Design

This is a post-market retrospective cross-sectional observational study of people using the Mosie Kit for at-home insemination. The goal of the study is to understand the pregnancy rate resulting from using the Mosie Kit of people with known fertility issues or those wishing to conceive without intercourse due to medical reasons such as vaginismus or being in a LGBTQ relationship desiring a child.

This study uses a convenience sample of people who purchased the Mosie Kit in the past 8 complete months prior to the commencement of the study. The complete known list of people will be invited to participate in the study. For the primary hypothesis 1, all study participants will be treated as one group initially. Subsequently, the study participants may be divided into groups according to their age, the type of relationships (heterosexual or LGBTQ), and/or source of infertility to examine the hypothesis as it relates to these subgroups if sufficient sample size indicates this is appropriate; this analysis corresponds to the tertiary hypothesis.

Primary hypothesis 1: Pregnancy rates using the at-home insemination Mosie Kit to deposit semen near or at the cervix (i.e. intracervical insemination) are equivalent or better than traditional in doctor's office intrauterine insemination.

Given the participants can either be people with fertility issues or people in LGBTQ relationships without known problems conceiving or single women wishing to conceive, another primary hypothesis that will be examined is the difference of pregnancy rates in each of these groups. Specifically, the primary hypothesis related to this is as follows:

Primary Hypothesis 2: Pregnancy rates of LGBTQ people or single women using the Mosie Kit where the female has no know fertility issues will be higher than that of heterosexual people with a known fertility cause or those that are designated as having an unexplained fertility issue.

The secondary hypothesis will examine the use of the Mose Kit and its safety as perceived and reported by the study participants. For these hypotheses the participants will be examined as one group as well as categorized by age group and type of relationship. Specifically, the secondary hypothesis will be as follows:

Secondary Hypothesis 1: The participants perceived the Mosie Kit to be easy to use for its intended purpose.

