This study does not use randomization. While no control group will be examined for the study, determining the result of some of the hypotheses is based on using the reported pregnancy rate of IUI in the literature. Specifically, the reported rate of pregnancy with IUI is as high as 20% in one cycle according to the American Pregnancy Association. According to the CDC, it can range between 10-35% across 6 cycles.

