9.1 Statistical Hypotheses and General Statistical Approach

The primary objective is to understand the outcome of using the Mosie kit for Intracervical insemination, i.e. pregnancy rate after its use. Specifically the hypothesis is as follows.

Primary hypothesis 1: Pregnancy rates using the at-home insemination Mosie Kit to deposit semen near or at the cervix (i.e. intracervical insemination) are equivalent or better than traditional in doctor's office intrauterine insemination (IUI). Conversely the null hypothesis is that the pregnancy rates using the at-home insemination Mosie Kit to deposit semen near or at the cervix do not have higher rates of pregnancy than in doctor's office IUI.

Analysis: Comparison of total rates of pregnancy using the Mosie Kit to the 10-20% rate reported for IUI by the American Pregnancy Association.

Primary Hypothesis 2: Pregnancy rates of LGBTQ couples or single women using the Mosie Kit where the female has no know fertility issues will be higher than that of heterosexual couples with a known fertility cause or those that are designated as having an unexplained fertility issue. The alternative hypothesis is that people with no known

fertility issues using the Mosie Kit will have less pregnancies than heterosexual couples with known fertility issues.

Analysis: Rate of pregnancy using the Mosie Kit will be obtained for the following groups: LGBTQ couples where carrying female has no known fertility issues, LGBTQ couples where carrying female has a known fertility issue, Heterosexual people with no known fertility issue, Heterosexual people with a known fertility issue, Single females with no known fertility issue and Single females with a known fertility issue. The rates of each group will be analyzed using descriptive statistics and the aggregate of the 3 groups with fertility issues will be compared with the aggregate of the 3 groups without fertility issues. An ANOVA will be used to compare the differences between groups.

Secondary Hypothesis 1: The participants perceived the Mosie Kit to be easy to use for its intended purpose. The alternative hypothesis is that the participants perceive the Mosie Kit to be difficult to use for its intended purpose.

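### Primary Hypothesis 1 claims equivalence or better against IUI, but its null is a superiority null and its comparator is a range with no reference value, margin or decision rule

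*Combined protocol and SAP*

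**What the plan says.** Section 4.1 states as Primary Hypothesis 1 that pregnancy rates with the kit "are equivalent or better than traditional in doctor's office intrauterine insemination". Section 9.1 repeats this and adds a null under which the kit's rates "do not have higher rates of pregnancy than in doctor's office IUI".

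The analysis given in 9.1 is a single line: "Comparison of total rates of pregnancy using the Mosie Kit to the 10-20% rate reported for IUI by the American Pregnancy Association". It names no test, no point within the range and no rule for success.

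Section 4.1 gives the comparator differently. From the same association, "the reported rate of pregnancy with IUI is as high as 20% in one cycle according to the American Pregnancy Association". From a second source, "it can range between 10-35% across 6 cycles". The endpoint table in section 3 defines the outcome over several cycles: "The primary endpoints is: Pregnancy Rate after up to 6 cycles".

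Section 9.4.1 sets significance at 0.05, with one-tailed tests for greater-than or less-than hypotheses and two-tailed tests for difference hypotheses. It does not cover equivalence or non-inferiority. The only margin in the documents is the survey margin of error in 9.2, which describes interval width.

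**The concern.** There are two faults.

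- **Hypothesis and null overlap.** If the two rates are equal, both statements are true. A test of the stated null can lead to a claim of superiority. It has no outcome that establishes equivalence, although equivalence is half of what is claimed.
- **The comparator is an interval, not a value.** A single observed rate can lie above one end and below the other. Without a named reference value or margin, the plan does not say what such a result means.

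There is no control group, so the choice of benchmark alone decides the comparison with IUI. Section 2.3.2 says the study will inform users how the kit's efficiency might compare with IUI, and sections 10.1.3 and 10.1.11 state an intent to publish. The per-cycle versus six-cycle mismatch in the IUI figures is a separate matter, and correcting it does not remove either fault.

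**Working it through.** **Inputs.** Target n = 500 and minimum n = 384 (9.2). Range 10-20% (9.1). Six-cycle range 10-35% (4.1). Significance level 0.05 (9.4.1).

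**The plan's own figures.** Half-width = 1.96 × √(0.25/n). For n = 500 this is 4.38 points and for n = 384 it is 5.00 points, matching the 4.4% and 5% in 9.2. These are precision figures and are not tied to any test of Primary Hypothesis 1.

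**Hypothesis against null.** Suppose 100/500 (20.0%) is observed and the reference is 20%. The exact one-sided p for a higher rate is P(X ≥ 100 | n = 500, p = 0.20) = 0.52. The null is retained, yet the observed rate equals the reference and could be described as equivalent. No step in the plan settles which description applies.

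**One result against both ends of 10-20%.** Take 75/500, so p = 0.15. The Wilson interval is [p + z²/2n ± z√(p(1−p)/n + z²/4n²)] / (1 + z²/n), with z = 1.96.
- z²/n = 0.00768, so the centre is (0.15 + 0.00384)/1.00768 = 0.1527.
- Half-width = 1.96 × √(0.000255 + 0.00000384)/1.00768 = 0.0313.
- 95% interval: 12.1% to 18.4%.
- Exact test against 10%: P(X ≥ 75) gives one-sided p = 0.0003.
- Exact test against 20%: P(X ≤ 75) gives one-sided p = 0.002.

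**How wide the zone is.** These are the counts whose Wilson 95% interval lies wholly inside the range:

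| n | Range | Counts | Observed rate |
|---|---|---|---|
| 500 | 10-20% | 64 to 82 | 12.8% to 16.4% |
| 384 | 10-20% | 50 to 61 | 13.0% to 15.9% |
| 500 | 10-35% | 64 to 154 | 12.8% to 30.8% |

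Exact (Clopper-Pearson) intervals for 10-20% give 13.0% to 16.4% at 500 and 13.3% to 15.9% at 384, so the method hardly matters.

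**Where the conflict ends.** At n = 500 the lower Wilson limit first exceeds 20% at 118/500 (23.6%), and first exceeds 35% at 196/500 (39.2%). From those rates upward, the result is above every value in the respective range. Between 83 and 117 of 500 (16.6% to 23.4%) the interval lies above 10% but includes 20%. The two ends then give no opposite significant results, but 9.1's null is rejected against 10% and retained against 20%.

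**What a margin would do (illustration).** The documents give none, so these margins are assumed: reference 20%, one-sided 0.025, exact test, true rate equal to the reference.

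| Assumed margin | Success at n = 500 | Power, n = 500 | Power, n = 384 |
|---|---|---|---|
| 3 points | ≥103 (20.6%) | 39% | 31% |
| 5 points | ≥92 (18.4%) | 83% | 71% |
| 10 points | ≥65 (13.0%) | >99.9% | >99.9% |

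The margin alone moves the success threshold at n = 500 from 13.0% to 20.6%.

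**The case against.** The stated objective is to understand the pregnancy rate, the sample size is precision-based, and reporting the rate with its interval is unaffected. This is true, and it confines the point to the claim against IUI. That claim is nevertheless labelled a primary hypothesis and has its own null.

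The observed rate may fall clear of the zone. The home-insemination results cited in section 2.2 are mostly higher: 13/29 (45%) over six cycles, 20/45 (44%), and 25% to 69% by age group. Those groups differ from kit buyers, many of whom may have used few cycles, so this does not settle the matter. It does show that the conflict is conditional on the rate.

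The plan's null and its one-tailed rule look only for a higher rate, so a finding of worse than IUI is not a planned verdict. This stands. The significantly-below result shows what the data could mean, not an analysis the plan schedules.

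A reader might infer more than the documents support:
- **That every rate inside the range supports better, equivalent and worse alike.** At 11% or 19% with n = 500, the 95% interval crosses one end of 10-20%.
- **That a rate significantly above 20% and below 35% shows the same conflict.** Section 4.1 ties the 20% to one cycle and the 35% to six, so that contrast belongs to the time-basis problem.
- **That the benchmark will be chosen after the rate is seen.** The plan does not say so; it only fails to prevent it.
- **That the results are destined for marketing.** Section 10.1.3 says only that the sponsor might use them so.

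**Conclusion.** The point holds with limits. The mismatch between hypothesis and null is plain in 9.1 and holds at any observed rate. The missing reference value and margin produce opposite significant results only in part of the range: 12.8% to 16.4% at n = 500 and 13.0% to 15.9% at n = 384 for 10-20%, or 12.8% to 30.8% at n = 500 for 10-35%. At about 23.6% or more (n = 500) the rate exceeds all of 10-20%, and at about 39.2% or more it exceeds all of 10-35%.

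These figures treat the completed surveys as a simple binomial sample and the quoted IUI rates as fixed values. Because this is the primary comparison, the wording should be settled before data are analysed.

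**What to change.** Before data are analysed, in sections 4.1 and 9.1:

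1. Name one IUI benchmark on the same time basis as the Mosie rate. The upper end of the quoted range is the conservative choice, because exceeding it means exceeding every quoted value. The documents do not themselves prefer it.
2. Claim a better rate only if the lower confidence limit exceeds that benchmark. State whether the limit is one-sided 95%, which agrees with the one-tailed 0.05 rule in 9.4.1, or comes from a two-sided 95% interval.
3. Delete the equivalence wording and write the hypothesis as the complement of the null.
4. If the sponsor keeps the equivalence-or-better claim, pre-specify a margin and rewrite the null as a rate below the benchmark by at least that margin. Restate in 9.2 what 384 to 500 surveys can deliver for it.
5. If the rule is not met, report the rate and its interval with no favourable claim against IUI.

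**Cost.** Steps 1 to 3 and 5 are wording, with 9.4.1 made consistent, and need no new data. Step 4 also reopens 9.2, since power may be low for a small margin. A favourable claim becomes harder to make. None of this cures self-selection of respondents or the lack of a concurrent control.

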Analysis: Descriptive statistics will be used to analyze perceived safety. Qualitative analysis will be used on any comments made related to safety. Rates of vaginal infections will be analyzed using descriptive statistics.

Secondary Hypothesis 5: The majority of participants indicate they have little to no safety concerns related to using the Mosie Kit. Alternative hypothesis is the majority of participants will be very concerned or extremely concerned about the safety of using the Mosie Kit.

Analysis: Descriptive statistics of self-reported level of concern. Additionally, safety measures such as hand washing, disposing of the syringe after use, and reading the instructions will be examined using descriptive statistics.

Tertiary Hypothesis 1: There will be higher pregnancy rates when using the Mosie Kit when the source of infertility is male-based than when it is female-based. The alternative hypothesis is there will be lower pregnancy rates when using the Mosie Kit when the source of infertility is male-based than when it is female-based.

Analysis: In addition to the descriptive statistics a t-test will be run to examine this hypothesis.

Tertiary Hypothesis 2: There is a difference in pregnancy rates of people with known fertility issues depending on the source of their infertility. Specifically, the following sources of infertility will be examined if sufficient data is available.

- o PCOS
- Endometriosis
- Low AMH or low ovarian reserve
- Low sperm count
- Sperm motility issues
- Unexplained infertility
- Erectile dysfunction
- Performance issues or sexual anxiety, or inability to orgasm with partner.

Page 27

- Vaginismus or vulvodynia
- Tilted uterus
- Multiple uterus/cervix
- Loss of a fallopian tube

The alternative hypothesis is that there will be no difference in the fertility rates associated with different sources of infertility.

Analysis: Descriptive statistics, t-test, correlations and multiple ANOVAs will be used to examine this hypothesis.

Tertiary Hypothesis 3: There will be a difference between individuals who perform 2 insemination instances as described in the instructions and those that follow a different schedule or dosage number. The alternate hypothesis is that there will be no difference between the individuals that perform the minimum 2 insemination instances and those that follow difference dosage schedule.

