9.4 Statistical Analyses

9.4.1 General Approach

Statistical analysis will commence with descriptive statistics for each survey question and plotting of the individual data into scatter plots to understand the data distribution. If any information suggests corrective procedures should be employed, the appropriate transformation or non-parametric test will be used.

Categorical values will be reported using descriptive statistics and frequency of occurrence. Key categorical values will also be converted into a percentage of total responses in order to allow an understanding of the prevalence of the response in the sample. For continuous variables, the means with standard deviations, median and range will be reported.

Qualitative data is only expected as a response to two questions, an open ended safety question and an additional comments question. The responses will be evaluated and categorized. Then the frequency of each category will be provided.

For inferential tests such as t-tests and ANOVAs, a p-value of 0.05 and a confidence interval of 95% will be used for statistical significance. The type of hypothesis will determine whether the specific tests will be one-tailed or two-tailed. Hypothesis seeking to understand whether there is or is not a difference will use a two-tailed test while those seeking a greater than or less than relationship will use a one-tailed test. Correlations among some of the variables will also be examined as appropriate.

Statistical analysis process for each hypothesis has already been described in section 9.1. No baseline analysis is used for cross-sectional studies. No interim analyses are planned for cross-sectional one survey studies.

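### Primary Hypothesis 2 and Tertiary Hypothesis 1 set higher against lower, with no null, no place for equality and no named tail, so the plan leaves open what would count as support

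*Combined protocol and SAP*

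**What the plan says.** Section 9.1 states each hypothesis, a competing statement and an analysis.

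- **Primary Hypothesis 2.** The claim concerns LGBTQ couples or single women in whom the female is free of recognised problems. It reads "know fertility issues will be higher than that of heterosexual couples with a known fertility cause or those that are designated as having an", and the sentence closes by adding infertility without an identified cause. The labelled alternative is that people with no known "fertility issues using the Mosie Kit will have less pregnancies than heterosexual couples with known fertility issues". For the analysis, six groups are described, the three with fertility issues are pooled and compared with the three without, and "An ANOVA will be used to compare the differences between groups".
- **Tertiary Hypothesis 1.** The claim: "There will be higher pregnancy rates when using the Mosie Kit when the source of infertility is male-based than when it is female-based". Against it stands this counter-statement: "The alternative hypothesis is there will be lower pregnancy rates when using the Mosie Kit when the source of infertility is male-based". The test: "In addition to the descriptive statistics a t-test will be run to examine this hypothesis".

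No null is labelled for either. Primary Hypothesis 1 is the only hypothesis in 9.1 that has one.

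Section 9.4.1 sets significance at 0.05. It makes tests two-tailed for hypotheses about whether a difference exists, while "those seeking a greater than or less than relationship will use a one-tailed test". It does not say in which tail the rejection region lies, nor what is concluded when the result is not significant.

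Section 9.2 justifies 500 surveys (minimum 384) by the precision of a single proportion. It gives no group sizes, rates or power for either comparison.

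**The concern.** A test needs a null that contains equality, an alternative that the data may come to support, and a stated rejection region. Here the study's expectation is one direction and the statement called the alternative is the other. The most likely uninteresting truth, that the groups do not differ, belongs to neither.

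The conclusion then depends on how the analyst reads the labels. Reading the named alternative in its textbook sense puts the rejection region at lower, and the study's claim takes the place of the null. Reading the claim as what is to be shown puts the region at higher, and the only written counter-statement after a non-significant result is that the first group does worse.

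This is one of two primary hypotheses. Section 10.1.11 commits to registry posting and intended publication, and Section 10.1.3 allows aggregate results to be used in marketing. With no power stated, a non-significant result is a realistic outcome, and the plan does not say how to report it.

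**Working it through.** **1. The plan's own figure.** The half-width for one proportion is 1.96 × √(0.25/n).

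- n = 500: 4.38%, matching the stated 4.4%.
- n = 384: 5.00%, matching the stated 5%.
- Inverted, 1.96² × 0.25/0.044² = 496 and 1.96² × 0.25/0.05² = 384.

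Section 9.2 therefore reproduces, but it concerns one overall percentage and says nothing about the error rate of a two-group comparison.

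**2. Does each pair cover all outcomes?** Write d for the rate in the group expected to do better minus the rate in the other group.

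| Hypothesis | Claim | Labelled alternative | Where is d = 0? |
|---|---|---|---|
| Primary 2 | d > 0 | d < 0 | in neither |
| Tertiary 1 | d > 0 | d < 0 | in neither |
| Tertiary 2 | d ≠ 0 | d = 0 | in the alternative |

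Tertiary Hypothesis 2 (like 3 and 4) becomes a complete pair once the labels are swapped. Primary Hypothesis 2 and Tertiary Hypothesis 1 do not: swapping gives null d < 0 and alternative d > 0, and equality is still missing.

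The two statements in Primary Hypothesis 2 also name different groups. The counter-statement is not restricted to LGBTQ couples and single women, and it leaves out unexplained infertility. The pooled comparison (three groups against three) is a further contrast.

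**3. Chance of upholding the claim when d = 0.**

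Inputs: alpha 0.05 (9.4.1) and N = 500 (9.2). Rates and splits are assumptions because the plan gives none: common rates of 10%, 20% and 35%; splits of 250/250, 150/350, 100/400 and 50/450.

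Test: pooled two-sample t on the 0/1 outcome, t = (p1 − p2) / (s × √(1/n1 + 1/n2)), with 200,000 simulations per setting.

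| Reading | Rule | Result when d = 0 |
|---|---|---|
| A. Labels taken formally | reject only toward lower; failure to reject counts as support | claim kept 94.9% to 96.1% (theory: 1 − 0.05 = 95%) |
| B. Claim is what must be shown | reject only toward higher | claim declared 5.0% to 5.9% (theory: 5%) |
| C. F test | non-directional | two-group F significant 4.6% to 5.0%, of which in the claim's direction 2.4% to 3.3%; six-group F significant 4.8% |

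The six-group figure uses 20,000 simulations, a common rate of 20% and assumed sizes of 60, 20, 130, 210, 50 and 30 (sum 500).

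**4. When the claim is wrong (15% against 20%).** Under Reading A, the analytic chance of rejecting toward lower is 0.431 at 250/250 and 0.294 at 100/400. The claim is therefore kept 1 − 0.431 = 57% and 1 − 0.294 = 71% of the time (simulated: 57% and 70%). Under Reading B it is declared in 0.1% and 0.2%.

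**5. When the claim is right.** Under Reading B, simulated power for 30% against 20% is 83% (250/250) or 68% (100/400). For 25% against 20% it is 38% or 30%. Non-significance would be common even with a true advantage of five points.

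**The case against.** The strongest reply is that the plan does not use *alternative* in its formal sense. Tertiary Hypotheses 2, 3 and 4 give that name to no difference or no effect. The t-tests and ANOVAs planned for 2 and 4 cannot reject in favour of no difference, so the word there must mean the competing statement if the expectation fails. Section 9.4.1 ties sidedness to what the hypothesis seeks, and both claims seek a higher rate, so an upper-tail test with about 5% error is at least as natural. An F test has no tail to choose.

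Much of this stands. A reader might infer that the plan, run as written, keeps its claim 95% of the time when nothing is going on. The documents do not support that. The 95% is simply 1 minus alpha under Reading A, and no rule says that a non-significant result upholds the claim. For Primary Hypothesis 2 the named test is not a one-tailed t-test, so Reading A fits Tertiary Hypothesis 1 better. A reader might also infer that every available verdict is false under equality. That goes too far, because reporting a result as not significant is not excluded.

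The reply does not repair the pairs. Under the charitable reading the upper-tail test has its usual error rate, but the only written statement opposing the claim is that the first group has fewer pregnancies. Nor does the F test help: Section 9.4.1 mentions ANOVAs in the same paragraph as the one-tailed rule, which leaves a directional claim, a non-directional test and an unnamed tail together.

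**Conclusion.** The concern holds as a misstated decision pair in both hypotheses. The null and the rejection tail are undefined, and the two written statements do not cover equality. Depending on a reading that the plan leaves open, the chance of upholding the claim when there is no difference is about 5% or about 95%. The higher figure requires both the formal reading of the labels and counting failure to reject as support; the documents neither require nor exclude that combination.

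On either reading, neither written statement is true when the rates are equal. For Primary Hypothesis 2 there is a further mismatch: an ANOVA does not test a directional claim.

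The 5% and 95% follow from alpha and barely change with the assumed sizes and rates. The 57% to 71% retention at 15% against 20%, and the power figures, do depend on those assumptions. The choice should be settled before the data are seen.

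**What to change.** In Section 9.1:

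1. **Primary Hypothesis 2.** Null: the rate in LGBTQ couples and single women with no known fertility issue is equal to or lower than the rate in heterosexual couples with a known or unexplained issue. Alternative: it is higher. Name a directional two-group comparison of proportions for exactly these groups, with rejection in the upper tail at 0.05. Keep the ANOVA and the pooled comparison as supportive.
2. **Tertiary Hypothesis 1.** Null: the rate with male-based infertility is equal to or lower than with female-based infertility. Alternative: it is higher. Name the upper tail.
3. **Both.** State that the claim is supported only if the null is rejected and is otherwise *not shown*. Report the difference in rates with its 95% confidence interval in either case.

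Primary Hypothesis 1 should not serve as the template: equality fits both its claim (equivalent or better) and its null (not higher).

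The cost is a few sentences and no new data. The downside for the sponsor is that both claims must now be shown, and a non-significant result cannot be reported as support.
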